2.1.3 Selected Other Secondary Objectives

1. To estimate the average duration of remission among participants.
2. To estimate the average time to first response among participants.
3. To estimate the average duration of response among participants.
4. To estimate the proportion of participants who maintain a state of remission from week 16 through week 52.

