2.2.3 Selected Other Secondary Endpoints/Variables

- Time to remission – Number of weeks after initiation that a subject first records a state of remission (CDAI score < 150). It will be calculated as the date on which remission is first observed minus the date of the first dosing date plus 1 day, divided by 7. For subjects still on study and not achieved remission at the time of assessment, time to remission will be censored at the date of the last assessment of CDAI score.
- Duration of remission – The number of weeks the subject is in remission (CDAI score < 150). It will be calculated as the first date following remission at which CDAI is ≥ 150 minus the date of remission, plus 1 day, divided by 7. Those subjects who experienced remission and continue to be in remission at the time of their last CDAI assessment will be censored at the date of their last CDAI assessment. Duration of remission will be calculated only for patients achieving remission.
- Time to response – Number of weeks after initiation that a subject first achieves a state of response (a reduction from baseline of ≥ 100 in CDAI score). It will be calculated as the date on which response is first observed minus the date of the first dose, plus 1 day, divided by 7. For those subjects who have not experienced response, time to response will be censored at the date of the last assessment of CDAI score.
- Duration of response – Time in weeks that a subject is in a state of response (a reduction from baseline of ≥ 100 in CDAI score). It will be calculated as the first date following response at which the reduction from baseline in CDAI is < 100 minus the date of response, plus 1 day, divided by 7. Those subjects who experienced response and continue to be in response at the time of their last CDAI assessment will be censored at the date of their last CDAI assessment. Duration of response will be calculated only for patients achieved response.
- Proportion of subjects experienced maintenance of remission (CDAI score < 150) from week 16 through week 52. Subjects experiencing a CDAI score ≥ 150 at any visit time point assessment between week 16 and week 52 or have no CDAI measurement week 16 or week 52 will be considered as having not achieved maintenance of remission.

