4.1.1 Study Visit Schedule

	Screening / Opt Screening / Visit Week 26 of RHB-104-01	Baseline Day 1 / Week 0 ²	Week 2	Week 4	Week 8	Week 16	Week 26	Week 39	Week 52	Week 56
Study Visit Window	(up to 21 days before BL if initial colonoscopy is performed)	Up to 21 days post SCR	± 3 days	± 3 days	± 7 days	± 7 days	± 7 days	± 7 days	± 7 days	± 7 days
Informed Consent	X									
Inclusion/ Exclusion Criteria Demography, Medical History	X	X								
Concomitant Medications Assessment		X ³	X	X	X	X	X	X	X	X
Vital Signs and Physical Exam.	X ¹	X	X	X	X	X	X	X	X	X
Adverse Event Assessments		X ³	X	X	X	X	X	X	X	
Diary Dispensing (AE/ConMed)		X	X	X	X	X	X	X	X	X
Steroid Status		X				X	X	X	X	X
CDAI assessment	X ¹				X	X	X	X	X	X
CDAI Diary Dispensing ⁴					X	X	X	X	X	
Subject Assessments: IBDQ and SF-36	X ¹					X	X		X	
Uveitis Assessment	X ¹		X	X	X	X	X	X	X	X
ECG ¹⁰	X ¹			X		X			X	X
Hematology and Biochemistry	X ¹		X	X	X	X	X	X	X	X
Urinalysis ¹¹	X ¹		X	X	X	X	X	X	X	X
C-Reactive Protein (CRP)	X ¹					X	X	X	X	
MAP Testing Blood (PCR) with Add'l Sample for Future Use	X ¹				X	X	X	X	X	X
MAP culture from blood	X ¹					X	X		X	
Fecal calprotectin	X ¹					X	X		X	
C. difficile Testing	X ¹						X		X	
Pregnancy Test Urine	X ¹	X	X	X	X	X	X	X	X	X
Optional Colonoscopy and CDEIS/SES-CD; store images		X ⁴				X ⁵			X ⁶	
IWRS Entry		X ⁷		X ⁸			X ⁹			
Study Drug Dispensing		X	X	X	X	X	X	X		
Dispensing of Drug Administration Instructions ¹²		X	X							
Drug Return & Accountability		X ¹³	X	X	X	X	X	X	X	
Review of stool sampling technique					X	X		X		
Telephone reminder of dose escalation		Day 7	Day 21							

¹ Procedure performed as part of RHB-104-01

² Baseline visit should be scheduled once the RHB-104-01 Wk26 / RHB-104-04 Screening CDAI score has been calculated (using RHB-104-01 Wk26 hematoctrit value).

³ Ongoing AEs/ConMeds from RHB-104-01 should be captured in RHB-104-04 eCRF (AEs & ConMeds for RHB-104-01 are captured in -01 eCRF up to day prior to -04 BL)

⁴ The colonoscopy must be performed on or before the Baseline or Week 0 Visit and must not interfere with CDAI data collection. If applicable, biopsies may be collected as part of the RHB-104-01 study.

⁵ In consenting subjects, colonoscopy must be performed up to 14 days after Visit Week 16.

⁶ In consenting subjects, colonoscopy must be performed a minimum of 8 days and a maximum of 20 days prior to visit Week 52.

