6.3 Outcome Analysis

The outcome analyses will be based on all ITT subjects.

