6.3.3 Selected Other Secondary Endpoints/Variables

6.3.3.1 Time to Event Endpoints/Variables Analysis

The Time to event endpoints that will be analyzed includes:

- Time to remission
- Duration of remission
- Time to response
- Duration of response

Kaplan Meier survival curves and parameters showing time-to-first observed response outcome will be summarized by parent study treatment, by anti-TNF use and overall. Summary statistics that will be presented will include minimum, maximum, the 25th and 75th percentiles, 95%

confidence intervals on the median (using the method of Brookmeyer and Crowley), and proportion of the events and censored data. Parent study treatment comparison will be performed using log-rank test.

Kaplan-Meier plots with descriptive summary statistics will be presented.

6.3.3.2 Remission from Week 16 through week 52

Number and proportion of subjects experiencing maintenance of remission (CDAI score < 150) from week 16 through week 52 and the number and proportion of subjects experiencing remission at week 16 and week 52 will be provided within each parent study treatment group and overall, as well as subgroup by anti-TNF agent use. 95% exact Clopper-Pearson confidence interval (CI) for the proportion will also be presented. Parent study treatment comparison will be performed using Fisher's exact test.

In addition, similar summaries will be provided for remission at week 52 overall and for subjects who achieved remission at week 16

Proportion of subjects who achieved the following response will be provided overall and by parent study treatment:

Remission at week 16 plus 50% reduction in CRP or calprotectin from baseline

Remission at week 52 plus 50% reduction in CRP or calprotectin from baseline

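### Time to response: subjects who leave before the first post-dose CDAI, including escalation failures, are censored at about time zero and never enter a risk set in an analysis labelled ITT

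*SAP*

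**What the plan says.** SAP 2.1.3 lists the objective "To estimate the average time to first response among participants", and SAP 6.3 states "The outcome analyses will be based on all ITT subjects". The tables and figures for these endpoints in SAP 8.1 carry the ITT label.

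SAP 2.2.3 measures time from the first dose, as event date minus first-dose date plus 1 day, divided by 7. For response the censoring rule is "For those subjects who have not experienced response, time to response will be censored at the date of the last assessment of CDAI score". For remission the rule also uses the final CDAI but is narrower: "For subjects still on study and not achieved remission at the time of assessment, time to remission will be censored at the date".

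SAP 6.3.3.1 plans Kaplan-Meier curves by parent treatment, by anti-TNF use and overall. On the outputs it says "Summary statistics that will be presented will include minimum, maximum, the 25th and 75th percentiles", a confidence interval for the median, "and proportion of the events and censored data". It adds "Parent study treatment comparison will be performed using log-rank test".

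The schedule in SAP 4.1.1 places CDAI at screening and at weeks 8, 16, 26, 39, 52 and 56, with the baseline visit "Up to 21 days post SCR". SAP 4.2 titrates former-placebo subjects over the first four weeks. It labels anyone who cannot reach the target dose a treatment failure and withdraws that subject.

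**The concern.** Escalation takes place in weeks 1 to 4, before any post-dose CDAI. A subject withdrawn then normally has only the screening CDAI, so the rule censors that subject at or before the start of follow-up. A subject whom the SAP calls a failure then counts neither as a non-responder nor as a person at risk.

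Kaplan-Meier assumes that a censored subject has the same later chance of response as those still observed. That is hard to defend when the reason for leaving is failure. If such subjects would have responded less often, the curve is too high and its percentiles are reached too early. In the log-rank comparison, the parent group with more early loss looks better. True titration happens only in the former-placebo group, so the loss may well be uneven.

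Two gaps in the specification do not depend on any rate. A subject who withdrew without remission has no censoring rule for time to remission. ITT subjects who were never dosed, whom SAP 6.1.2 foresees, have no time origin for either endpoint.

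**Working it through.** **1. The plan's own figure.** The documents state no figure for time to response. The only design figure is in SAP 6.1.7: a maximum exact 95% interval width of 0.203 at N = 100. For 50 of 100 the Clopper-Pearson limits are 0.3983 and 0.6017, a width of 0.2034, so the figure reproduces. It gives a yardstick of about 10 points for the half-width.

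**2. Censoring time.** Let d be the days from screening CDAI to first dose. The SAP formula gives (-d + 1)/7 weeks:
- d = 0: +0.14
- d = 7: -0.86
- d = 14: -1.86
- d = 21: -2.86

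The week 8 visit has a window of ±7 days, so the first scheduled chance of an event is about week 7. Every value above lies before it.

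**3. Effect on the curve.** With L subjects censored before the first event, N - L are at risk at week 8. If nobody else is censored before the last event, the curve ends at R/(N-L). The proportion of enrolled subjects is R/N, so the gap is the curve's final value times L/N. Example with assumed counts N = 100, R = 50, L = 10: 50/90 = 0.556 against 0.500.

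**4. Size at week 52.** All rates are assumptions. The chance of first response among those at risk at weeks 8, 16, 26, 39 and 52 is h = 15, 15, 12, 10, 8% (lower case) or 30, 20, 15, 10, 8% (higher case).
- Lower curve: 1 - 0.85 × 0.85 × 0.88 × 0.90 × 0.92 = 47.36%
- Higher curve: 1 - 0.70 × 0.80 × 0.85 × 0.90 × 0.92 = 60.59%

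| Early leaving | Lower: % of enrolled | Gap (points) | Higher: % of enrolled | Gap (points) |
|---|---|---|---|---|
| 2% | 46.41 | 0.95 | 59.38 | 1.21 |
| 5% | 44.99 | 2.37 | 57.56 | 3.03 |
| 10% | 42.62 | 4.74 | 54.53 | 6.06 |

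**5. Percentiles.** In the higher case the curve reaches 52.4% at week 26, so the median is week 26. With 10% early leavers kept as non-events, 47.16% have responded by week 26 and 51.44% by week 39, so the median becomes week 39.

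**6. Later withdrawal.** With 5% early leaving, and a further 5% of remaining non-responders lost after each visit, 41.91% (lower) and 54.87% (higher) of enrolled subjects have a recorded response. The gaps are 5.4 and 5.7 points. R/(N-L) is then a floor for the end of the curve.

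**7. Between parent groups.** Assume 50 subjects and 20 responders in each group, so R/N = 0.400 in both. With L = 10 in one group and L = 2 in the other, the curves end at 20/40 = 0.500 and 20/48 = 0.417.

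**The case against.** Censoring at the last assessment is the usual convention, and the curve is right if leavers would have responded like stayers. A Kaplan-Meier estimate normally differs from the crude event fraction once subjects are censored early. That difference is not in itself a defect, and the plan shows the proportion censored beside the curve. This stands. What remains is that the SAP does not say it wants the hypothetical rate without dropout, and its own failure label argues against non-informative censoring.

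A reader might infer that the curve always equals R/(N-L). It does so at week 8 (with R the responders at that visit) and at the end only if nobody else is censored before the last event.

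A reader might also infer a contradiction with the week 16 rates, where missing counts as failure (SAP 2.2.2, 6.1.3). Those are rates at a visit, not cumulative first response, so this is a difference of approach.

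Nor do the documents support calling every withdrawal a failure. SAP 4.2 gives that label to escalation failures. Rescue use is covered separately in SAP 2.2.1 and 6.1.6 and is not part of this point. The share of L made up of escalation failures is unknown.

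Some assumed percentile shifts are threshold effects and should carry no weight. At 5% early leaving the higher case gives 49.78% at week 26, and at 10% the lower case gives 24.98% at week 16. In 100 whole subjects these are 50 and 25.

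Finally, an early-termination CDAI may exist in procedures not supplied here; ET appears among the SAP abbreviations, though the schedule shows no such visit. A CDAI without response taken before the week 8 window would still leave the subject out of every scheduled risk set.

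**Conclusion.** The point holds. The stated rule removes subjects who leave before week 8 from every risk set, unless they have an unscheduled CDAI that shows response or falls in the week 8 window. They include subjects the SAP itself calls failures, and no other section repairs this. The likely effect is an upward bias in the time-to-response curve, its percentiles and the position of the parent group with more early loss. It rests on leavers being less likely to respond than stayers.

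With assumed early leaving of 2 to 10% and no later withdrawal, the week 52 gap is about 1 to 6 points, against an interval half-width of about 10 points at N = 100. Even 43 responders with 10 early leavers give overlapping exact intervals: 43/100 = 43.0% (33.1 to 53.3) and 43/90 = 47.8% (37.1 to 58.6).

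A reader might infer that the main efficacy result is at risk. It is not: week 16 remission and response count missing as failure. These are third-tier endpoints, and the log-rank test is exploratory, since the protocol synopsis foresees no formal comparison between groups. Disposition by parent group (SAP 6.2.1) would show uneven loss, but it would not correct the curve. Severity is minor to should-fix.

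**What to change.** - State one rule for both time to response and time to remission. Keep escalation failures as non-events to week 52, or estimate cumulative incidence with discontinuation as a competing event.
- Apply the same handling to other subjects with no post-baseline CDAI, at least as a parallel analysis.
- Report cumulative first response and first remission at weeks 8, 16, 26, 39 and 52 on the ITT denominator, with exact intervals. This is needed because retaining only the early leavers does not remove the effect of later censoring. With N = 100, R = 50 (20, 15, 10, 3 and 2 at the five visits), L = 10 kept and 10 later dropouts censored at week 8, the curve still ends at 0.543 and not 0.500.
- Keep the censored Kaplan-Meier curve alongside.
- Define day 0 for never-dosed ITT subjects, for example the baseline visit date or, failing that, the enrolment date, and rule out negative times. Otherwise dropped records could change the denominator unnoticed.

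The cost is SAP wording and modest programming, with no new data. The curves will look slightly less favourable.

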6. STATISTICAL METHODOLOGY

6.1 Statistical and Analytical Issues

6.1.1 Statistical Methods

In general, if there is disagreement between this SAP and the statistical methods outlined in the protocol, the SAP would supersede the protocol.

Descriptive statistics summary results will be produced and presented for all the data collected on the different assessments that include demographics, baseline characteristics, concomitant medications, outcome, and safety endpoints. Continuous data summary descriptive statistics will include the number of observations, means, standard deviations, medians, and ranges. Categorical variables will be summarized with frequencies and percentages or specified otherwise.

In the parent study, there was one randomization stratification factor, use of protocol permitted anti-TNF agents (yes/no). In the current study, treatment comparisons will be performed without taking this stratification factor into consideration unless specified otherwise.

All statistical analyses will be performed using SAS statistical software (Version 9.4 or an updated latest higher version available at the time of analysis). Adverse events will be coded using the most recent MedDRA version available at the time of analysis. Concomitant medications will be coded using the most recent version of World Health Organization (WHO) Drug dictionary. The actual version of each dictionary will be footnoted in the respective outputs.

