6.1.3 Missing Data and Handling of Dropouts

All available outcome and safety data will be included in data listings and tabulations.

CDAI Missing Data:

The computation of CDAI requires 7 days of consecutive diary daily data. For subjects with CDAI diary data reported that is less than 7 days of data, the reported data will be standardized to 7 days by dividing the sum of CDAI score over the number of days of data by total number of days of reported data multiplied by 7. If less than 4 days of diary data is available, the subject will be categorized as a non-responder and the CDAI score will be considered missing. As specified in section 2.2, subjects with missing assessment will be assumed to not be in a state of remission/success for each scheduled visit (week 16, 26, or 52).

Handling of missing date information for AEs:

The term *missing date* refers to a completely missing date or to partial date where month or/and day or/and year is/are missing, e.g. missing month/day/year. Missing start and end dates will be imputed conservatively, i.e. missing values will be imputed in such a way that the duration of the AE is considered with the longest possible duration. The missing start date and end date of AE will be imputed for the purpose of defining treatment emergent adverse events (TEAE) and for assigning events to treatment periods using the following definitions:

(i) Adverse Event Start Date:

Event Missing Day: If Adverse event day is missing but month and year present, then impute the 1st of the month unless month and year are the same as first dose of study drug then impute day first day of dose.

Event Missing day and month – If adverse event day and month both are missing but year is present then impute 1st January unless year is the same as first dose date then impute day and month first dose day and month.

Completely missing – impute first dose date unless the end date suggests it could have started prior to this in which case impute the 1st January of the same year as the end date.

(ii) Adverse Event End Date:

Missing day – If AE day is missing but month and year is present then impute the last day of the month.

Missing day and month – If AE has missing day and month but year is present then impute 31st December.

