Table 14.2.7	Inflammatory Bowel Disease Questionnaire (IBDQ) Score at Baseline, Week 16 and Week 52: Intent-to-Treat Population
Figure 14.2.7.1	Bar Graphs of IBDQ Total Score at Baseline, 26 and 52 weeks by Treatment group: Intent-to-Treat Population
Figure 14.2.7.2	Bar Graphs of IBDQ Sub Score at Baseline, 26 and 52 weeks by Treatment group: Intent-to-Treat Population
Inflammation Assessment	
Table 14.2.8.1.1	Summary Serum Marker of Inflammation (CRP) Level: Intent-to-Treat Population
Table 14.2.8.1.2	Summary Stool Marker of Inflammation Level - Fecal calprotectin: Intent-to-Treat Population
Table 14.2.8.2.1	Proportion of subjects with CRP Marker of Inflammation Normal/High by Visit: Intent-to-Treat Population
Table 14.2.8.2.2	Proportion of subjects with Fecal calprotectin Normal/High by Visit : Intent-to-Treat Population
Table 14.2.8.3.1	Shift in Serum Marker of Inflammation (CRP) Status Normal/High from Baseline to Weeks 16, 26, 39 and Week 52: Intent-to-Treat Population
Table 14.2.8.3.3	Shift in Stool Marker of Inflammation (Fecal calprotectin) Status Normal/High from Baseline to Weeks 16, 26 and Week 52 : Intent-to-Treat Population
Additional endpoints	
Table 14.2.9.1	Summary of CDAI Score by Visit: Intent-to-Treat Population
Table 14.2.9.2	Summary of PRO-2 Score by Visit: Intent-to-Treat Population
Adverse Events	
Table 14.3.1.1.1	Adverse Events Incidence Summary: Safety Population
Table 14.3.1.1.2	Adverse Events Incidence Summary by Anti-TNF Use: Safety Population
Table 14.3.1.2.1	Treatment-Emergent Adverse Events by System Organ Class and Preferred Term: Safety Population
Table 14.3.1.2.2	Treatment-Emergent Adverse Events by System Organ Class and Preferred Term by Anti-TNF Use: Safety Population
Table 14.3.1.2.3	Summary of Treatment-emergent Adverse Events Occurring in at Least 5% of Subjects by System Organ Class and Preferred Term in Descending Frequency
Table 14.3.1.2.4	Summary of Treatment Related Treatment-emergent Adverse Events Occurring in at Least 5% of Subjects by System Organ Class and Preferred Term in Descending Frequency
Table 14.3.1.3	Treatment-Emergent Adverse Events by System Organ Class, Preferred Term, and Relationship to Study Medication: Safety Population
Table 14.3.1.4	Treatment-Emergent Adverse Events by System Organ Class, Preferred Term, and Maximum Severity: Safety Population

Table 14.3.1.5	Treatment-Emergent Adverse Events Leading to Study Discontinuation by System Organ Class and Preferred Term: Safety Population

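### Maintenance of remission, weeks 16 to 52: SAP 2.2.3 lets a missing week 26 or week 39 CDAI pass, while SAP 6.1.3 assumes no remission at a missing week 26 and leaves out week 39

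*SAP*

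**What the plan says.** The endpoint comes from item 4 of SAP 2.1.3: "To estimate the proportion of participants who maintain a state of remission from week 16 through week 52". The protocol's outcome definition covers the same span and has no rule for missing visits.

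SAP 2.2.3 gives two ways to fail. One is a CDAI of 150 or more at any visit from week 16 to week 52. The other is a missing score, but only at the two ends: subjects who "or have no CDAI measurement week 16 or week 52 will be considered as having not achieved maintenance of remission". SAP 2.2.1 and 6.1.6 add a third route, because new or increased treatment for Crohn's disease counts as failure in remission analyses.

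SAP 6.1.3 sets a general rule: "subjects with missing assessment will be assumed to not be in a state of remission/success for each scheduled visit (week 16, 26, or 52". It introduces this rule as something already specified in section 2.2. It also says that with fewer than 4 diary days "the subject will be categorized as a non-responder and the CDAI score will be considered missing".

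The row "CDAI assessment" in SAP 4.1.1 is marked at weeks 16, 26, 39 and 52, so two scheduled scores lie between the end visits.

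SAP 6.3.3.2 reports maintenance with an exact Clopper-Pearson interval and a Fisher test by parent-study arm. Separately, "the number and proportion of subjects experiencing remission at week 16 and week 52 will be provided".

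**The concern.** Maintenance is meant to say more than being in remission at both ends. If the middle visits may be missing, a subject with no score at week 26 or week 39 is called maintained on the same two scores that satisfy the separate week 16 and week 52 summary.

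The two SAP sections do not fit together. The SAP assumes a subject with no week 26 score is not in remission at week 26, yet 2.2.3 can call that subject in remission from week 16 through week 52. No text says whether the 6.1.3 visit status feeds the composite endpoint. The only precedence statement, in SAP 6.1.1, is that "if there is disagreement between this SAP and the statistical methods outlined in the protocol, the SAP would supersede the protocol"; it does not rank one SAP section over another. Two programmers could therefore classify the same subject differently in Table 14.2.3.1.

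For the overall rate the direction is fixed: allowing gaps can raise it or leave it unchanged, never lower it. A gap does not need a missed visit, because too few diary days also makes the score missing.

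**Working it through.** **1. The plan's own figure.** SAP 6.1.7 gives a maximum exact 95% interval width of 0.203 at 100 subjects and 50% success. For 50/100 the Clopper-Pearson limits are 0.3983 and 0.6017, a width of 0.2034. The figure reproduces. It does not bear on the present point, but the same interval method is used below.

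**2. The rules side by side.** Take a subject with CDAI below 150 at weeks 16 and 52, no observed score of 150 or more between them, and no rescue failure.

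| Missing CDAI | 2.2.3 as written | 6.1.3 visit status carried in | Missing at any of the four visits fails |
|---|---|---|---|
| none | maintained | maintained | maintained |
| week 26 | maintained | not maintained | not maintained |
| week 39 | maintained | visit list silent | not maintained |
| weeks 26 and 39 | maintained | not maintained | not maintained |

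Subjects with no week 16 or week 52 score fail in every column, so dropout before week 52 plays no part. The middle column depends on carrying the visit status into the endpoint, which the SAP neither orders nor rules out.

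**3. The cross-reference.** SAP 6.1.3 says it repeats section 2.2. Section 2.2 gives missing-CDAI rules for week 16 (2.2.1 and 2.2.2) and for weeks 16 and 52 (2.2.3). It gives none for week 26.

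**4. Where the week 26 rule could apply.** The remission outputs listed in SAP 8.1 use week 16, week 52, the span from 16 to 52, or time-to-event methods based on observed scores and censoring. Only the span could use an assumed week 26 status. If 2.2.3 stands alone, the 26 in the 6.1.3 list affects no planned remission table.

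**5. Illustrative size.** The documents give no missed-visit rate and no expected maintenance rate. Assumptions: N = 100 (SAP 6.1.7); K = 20 subjects pass 2.2.3; a share p of those K lacks a CDAI at a given middle visit, with p = 0.05, 0.10 or 0.15.

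- Week 26 alone: K × p = 1, 2 or 3 subjects change class.
- Weeks 26 and 39 together: between K × p (the same subjects miss both) and 2 × K × p (different subjects), that is 1–2, 2–4 or 3–6. Under independence, K × [1 − (1 − p)²] = 1.95, 3.80 or 5.55.

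| p | 2.2.3 as written | Missing week 26 fails | Missing week 26 or 39 fails (largest change) |
|---|---|---|---|
| 0.05 | 20% (12.7–29.2) | 19% (11.8–28.1) | 18% (11.0–26.9) |
| 0.10 | 20% (12.7–29.2) | 18% (11.0–26.9) | 16% (9.4–24.7) |
| 0.15 | 20% (12.7–29.2) | 17% (10.2–25.8) | 14% (7.9–22.4) |

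Brackets hold exact 95% limits. Every revised rate lies inside the 12.7–29.2 interval.

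**6. Other assumptions.** With K from 20 to 40 and 2 to 10% missing independently at each visit, the largest difference between the rules runs from 20 × (1 − 0.98²) = 0.8 to 40 × (1 − 0.90²) = 7.6 percentage points.

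**The case against.** The strongest reply is that 2.2.3 is specific to this endpoint and can be programmed as it stands. It speaks of any visit for an observed relapse and then names only the two end visits for missing data, which may be deliberate. Section 6.1.3 sets status visit by visit and claims only to restate section 2.2, so its 26 may be a stray number. This stands in part: 2.2.3 may well be the natural text to follow. It does not remove the need for a correction, because either the cross-reference is wrong or 2.2.3 is incomplete.

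A second reply is that allowing gaps matches duration of remission, also in 2.2.3, which ends at the first observed score of 150 or more and so runs through a missed visit. That is correct. Under the stricter rule a subject could have unbroken remission duration and still be not maintained. It is a reason to state the difference openly, and a fair argument for a sponsor who prefers to allow gaps.

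A third is that gaps can be traced through Listings 16.2.6.1 and 16.2.6.2 and the table "Summary of CDAI Score by Visit: Intent-to-Treat Population". They can, but no planned table is described as counting maintained subjects who have a gap.

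A reader might infer that the SAP flatly contradicts itself. The documents do not support that: 2.2.3 is silent on weeks 26 and 39, and the clash at week 26 arises only if the 6.1.3 status is carried into the endpoint. Nor do they show a settled difference in treatment between weeks 26 and 39, because the sentence on fewer than 4 diary days names no visit.

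**Conclusion.** The point holds as a minor misalignment within the SAP. Section 2.2.3, by omission, counts as maintained a subject with a week 26 or week 39 gap who meets every other condition, including no rescue failure. Section 6.1.3 assumes no remission at a missing week 26 and does not list week 39. Relative to the missing-equals-failure convention the SAP uses at weeks 16 and 52, the 2.2.3 rule can only raise the overall maintenance rate.

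The size is unknown. The fall from 20% to between 19% and 14% rests on assumed values: 100 subjects, 20 passing, and 5 to 15% of those missing each visit.

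A reader might infer that the efficacy conclusions are at risk, or that every subject with a gap is counted as maintained. Neither follows. The primary and key secondary endpoints have their own explicit week 16 rules and are untouched. Only subjects seen in remission at both week 16 and week 52 can change class, and the endpoint sits in the selected other secondary group.

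**What to change.** In SAP 2.2.3, state that a missing CDAI at any of weeks 16, 26, 39 or 52 counts as not having maintained remission. In SAP 6.1.3, make the visit list weeks 16, 26, 39 and 52, so that its reference to section 2.2 becomes accurate for this endpoint.

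In Table 14.2.3.1, add a labelled sensitivity row for the gaps-allowed rule, with the number of subjects whose class differs. Add a note that duration of remission uses observed scores and runs through a missed visit, so the two endpoints may differ for such subjects.

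If the sponsor prefers gaps-allowed as the main rule, 2.2.3 should say so expressly, 6.1.3 should say that its visit status does not feed this endpoint, and the stricter rule should become the sensitivity row.

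The cost is one sentence in 2.2.3, one added visit in 6.1.3, and one or two table rows with a footnote. The downside of the stricter rule is that the reported rate may fall slightly and be conservative for subjects who were truly in remission at a missed visit.
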